### **8.3 Statistical methods**

The statistical analysis of study outcomes will primarily be descriptive. Outcomes will be assessed via the baseline and follow-up surveys, and whether or not self-sampling kits were returned by participants in the intervention arm. The main outcome is the differences in overall cervical cancer screening rate and the overall colorectal cancer screening rate at the end of the study between the two arms. Analysis of the main outcomes will be evaluated with a Fisher's exact test. Demographics of the patients in the two groups will be compared.

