### 1.2 Primary Study Endpoints

Differences in overall cervical cancer screening rate and the overall colorectal cancer screening rate at the end of the study between the two arms.

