#### **3.3.2 Follow-up for withdrawn subjects**

The withdrawal will be documented and the subject will be replaced if the timeline allows.

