### **7.2.5 Follow-up survey- Week 10**

Participants will complete the follow-up survey with a member of the study team via phone. This will occur regardless of whether the participant was in the intervention or the control arm, and regardless of whether the participant completed and returned the self-sampling kits if in the intervention arm.

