### **7.4.4 Subject Compliance Monitoring**

Subject compliance will be confirmed once their lab results are received from the Penn State Heath Clinical lab.

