### **7.4.5 Blinding of the Test Articles**

Not applicable.

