## **8.0 Subject Numbers and Statistical Plan**

### **8.1 Number of Subjects**

We plan to contact 500 potentially-eligible women via mail and email using the initial invitation letter. Of these, 220 are planned to consent and complete the baseline survey. From this 220, 110 will be randomized to the control group and 110 will be randomized to the intervention group. We expect about 10% loss to follow-up over the study period.

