### **8.2 Sample size determination**

This is a pilot study to approximate the rates of colorectal and cervical screening in the two study arms. Should the intervention yield a screening rate of 40% and the control arm a screening rate of 20%, then the proposed sample sizes yield 80% power based on a two-sided Fisher's exact test and a 2.5% type-1 error rate (allowing for two co-primary endpoints). The results of this pilot study will inform us with more accurate assessments of these screening rates so that future, more accurately powered studies can be conducted.

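### Section 8.3 adds kit return as an outcome source in the intervention arm only and gives no rule for missed week-10 surveys, which can shift both co-primary differences by up to about 2.6 points in the cases examined

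*Combined protocol and SAP*

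**What the plan says.** Section 1.2 sets the co-primary endpoints: "Differences in overall cervical cancer screening rate and the overall colorectal cancer screening rate at the end of the study between the two arms". Because the rates are overall rates, screening by any route should count, including a control woman's test at her clinic.

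Section 8.3 names the data sources: "Outcomes will be assessed via the baseline and follow-up surveys, and whether or not self-sampling kits were returned by participants in the intervention arm". The two arms are then compared with Fisher's exact test. The follow-up survey in 7.2.5 is a week-10 phone call made "regardless of whether the participant was in the intervention or the control arm". Section 8.1 adds: "We expect about 10% loss to follow-up over the study period".

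Kit status can be known without the call. On compliance, 7.4.4 says: "Subject compliance will be confirmed once their lab results are received". Section 12.0 has those results sent to the study team. The electronic health record appears in 4.1 and 4.2.2 for finding and recruiting women, not as an outcome source.

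The documents do not say how a woman without a week-10 survey is scored, which women are analysed, or whether a returned kit counts when the call is missed. Section 3.3.2 comes closest, on withdrawals: "The withdrawal will be documented and the subject will be replaced if the timeline allows". That is a recruitment rule, not an analysis rule. Section 22.0 refers to a separate data plan form that was not supplied.

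**The concern.** The plan as written has two routes to a positive outcome in one arm and one route in the other. The routes part company when the week-10 call is missed. An intervention woman who misses it can still be counted from her kit. A control woman who was screened at her clinic and misses it cannot be counted at all.

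The effect on the difference depends on a scoring rule that the plan leaves open, and the rule could be chosen after the data are seen. The estimate is the main product here. Section 8.2 says: "This is a pilot study to approximate the rates of colorectal and cervical screening in the two study arms", so that later studies can be better powered. A systematic shift in these rates would carry over into those designs.

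A smaller gap sits beside this one. Section 8.3 counts kits that were returned, while 7.4.4 looks to laboratory results for compliance. Neither says whether a returned kit must give a valid result to count as screening.

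**Working it through.** **Inputs from the documents.** 110 per arm and about 10% loss (8.1); 40% against 20%, two-sided Fisher's exact test at 2.5% per endpoint, 80% power (8.2).

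**Assumptions.** Loss is L = 0.10 in each arm and unrelated to screening. The share of intervention-arm screening done by study kit, k, is not in the documents; it is shown as all (k = 1) and half (k = 0.5).

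**1. The plan's own figure.** Exact Fisher power for 40% against 20% at 110 per arm is 81.3%, which agrees with the stated 80%. With 99 per arm (110 × 0.90) it is 76.3%.

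**2. What the named sources can see.**
- Intervention women known to be screened: 0.40 × [k + (1 − k) × 0.90] = 0.36 + 0.04k, as a fraction of all randomized.
- Control women known to be screened: 0.20 × 0.90 = 0.18.

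**3. Expected difference under four scoring rules (truth: 20 points).**

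| Rule | Formula | k = 1 | k = 0.5 |
|---|---|---|---|
| A. Missed survey and no kit = unscreened, both arms | (0.36 + 0.04k) − 0.18 | 22.0 | 20.0 |
| B. Women with neither source dropped, both arms | (0.36 + 0.04k)/(0.90 + 0.04k) − 0.20 | 22.6 | 21.3 |
| C. Lost controls dropped, all intervention women classified | (0.36 + 0.04k) − 0.20 | 20.0 | 18.0 |
| D. Survey completers only, both arms | 0.40 − 0.20 | 20.0 | 20.0 |

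For B, the arithmetic is 0.40/0.94 = 42.55% at k = 1 and 0.38/0.92 = 41.30% at k = 0.5. At a fixed kit share the rules span 22.55 − 20.0 = 2.55 points (k = 1) or 21.3 − 18.0 = 3.3 points (k = 0.5).

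Rule A equals 18 + 4k points. It exceeds 20 only when k is above one half, and falls short of 20 when k is below one half.

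**4. No true difference, k = 1.** Under rule A the spurious gap is p − 0.90p = 0.10p.
- At 20% in both arms: 2 points, Fisher rejection rate 2.5%.
- At 40% in both arms: 4 points, Fisher rejection rate 3.9%.

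The nominal level is 2.5%. With k = 0.5 the gaps halve to 1 and 2 points and the error is 1.9% and 2.2%. Under rule D there is no gap and the error is 1.6% to 1.7%.

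**5. Scale.** The standard error of the difference at 110 per arm is √[(0.40 × 0.60 + 0.20 × 0.80)/110] = √(0.40/110) = 6.0 points. The largest shift in the table is 2.55/6.0 = 0.42 of a standard error.

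**6. Bounds with 11 lost per arm and all randomized women in the denominator.** At k = 1, women lost without a kit are 0.10 × 0.60 = 0.06 of the intervention arm.
- Worst case: 0.40 − (0.18 + 0.10) = 12 points.
- Best case: (0.40 + 0.06) − 0.18 = 28 points.

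At k = 0.5 the bounds are 10 to 28 points. From the survey alone they are 8 to 28.

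**7. How far completers-only can be trusted.** Suppose unscreened women are twice as likely to be lost (an assumption), with 10% loss overall. Rule D then gives 41.67% − 20.99% = 20.7 points if this holds in both arms, and 41.67% − 20% = 21.7 points if it holds in the intervention arm only.

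**The case against.** The strongest reply is that this is a small, mainly descriptive pilot. A 95% interval for the difference is about ±12 points (1.96 × 6.0), so a shift of 2 to 3 points would be hard to see. At the planned 20% control rate the null error is about 2.5% or less under every rule. The 3.9% figure needs 40% true screening in both arms, twice the planned control rate, with all intervention screening by kit. All of this stands, and it limits the importance of the point. It does not remove it, because the shift is systematic and a larger later study would inherit it.

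Three stronger readings are tempting, and the documents do not support them.

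- A reader might infer that the extra source always favours the intervention. It does not: rule A gives exactly 20 points at k = 0.5 and less below that, and rule C works against the intervention when some of its screening is done outside the kit.
- A reader might join the 18 and the 22.6 into one range caused by the scoring rule alone. Those two ends belong to different kit shares, and the 18 needs a rule that treats the arms differently. Among the rules in the table that treat both arms alike, the half-kit range is 20 to 21.3. Scoring the survey alone, with missed calls as unscreened, also gives 0.36 − 0.18 = 18, but that sets aside the kit source that 8.3 names. Nor are these figures outer limits, as the bounds show.
- A reader might add bias from over-reporting on the survey or from unusable kits. The documents give no rate for either, so no size is claimed here.

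It is also fair to say that completers-only is one choice among several. It sets aside some laboratory-documented kit returns.

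**Conclusion.** The point holds, as a modest one that should be fixed. Following 8.3 as written ascertains both co-primary endpoints differently by arm, and the supplied text has no rule for a missed week-10 survey. With equal 10% loss unrelated to screening and a true 40% against 20%, the expected difference is 20 to 22.6 points if all intervention screening is by kit and 18 to 21.3 if half is. Direction depends on the scoring rule and on the kit share, which is unknown. The two-source structure and the missing rule are matters of text and do not depend on these assumptions; the sizes do.

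**What to change.** In 8.3, for each test separately:

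1. Define *screened* as a valid laboratory result on a study kit, or that test reported on the week-10 survey as done outside the study, from randomization to week 10 in both arms. State one missed-survey rule in advance and apply it to both arms, for example survey completers only.
2. Beside it, in the same women, compare the identical week-10 survey item alone between arms. The gap between the two results shows what the one-arm kit source adds.
3. Report best-case and worst-case bounds with all randomized women in the denominator, including any who withdraw and are replaced. Use here the kit results of women who missed the call.

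The cost is protocol wording and a little more analysis, since the laboratory results already reach the team. If completers-only is chosen, power at 40% against 20% is about 76% rather than 81%, and about 4 kit returners (40% of 11, if all intervention screening is by kit) move from the main comparison to the bounds. That rule is unbiased only if loss is unrelated to screening, which is why the bounds belong beside it, although they are wide. The survey must ask about each test, where it was done and when. The survey was not supplied, so items may have to be added before follow-up calls begin.

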## **3.0 Inclusion and Exclusion Criteria**

### **3.1 Inclusion Criteria**

1. Female
2. 50-65 years of age at time of study enrollment
3. Lives in rural, segregated county of Pennsylvania
4. Able to speak, read, and communicate well in English
5. Out of date for both cervical and colorectal cancer screening
6. Active patient at selected Primary Health Network clinics

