## **4.0 Recruitment Methods**

### **4.1 Identification of subjects**

Potentially-eligible women will be identified from the electronic health record (EHR) of partner FQHC clinics by an employee of the FQHC.

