### **7.2.2 Randomization- Week 0**

Once a participant has completed the baseline survey, she will be randomly assigned to either the control arm or the intervention arm by a member of the study team. A simple randomization scheme, with 1:1 randomization, will be used to ensure equal sample sizes in the intervention and control arms.

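### Control-arm screening rests on telephone self-report alone while the intervention arm also has kit returns, so the two co-primary rates are measured on unequal evidence and the control rate is open to bias

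*Combined protocol and SAP*

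**What the plan says.** Section 1.2 makes the between-arm differences in cervical and in colorectal screening rates the primary endpoints. On how screening is measured, section 8.3 states "Outcomes will be assessed via the baseline and follow-up surveys", together with whether kits came back from the intervention arm. Section 7.2.5 adds: "Participants will complete the follow-up survey with a member of the study team via phone". That call takes place in both arms at week 10, whether or not kits were returned. Under section 7.4.4, kit use is confirmed by laboratory results. Control women receive only a letter (7.2.3), so the survey is their sole stated source of outcome.

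Electronic health records appear only for finding and recruiting women. Potentially eligible women "will be identified from the electronic health record (EHR) of partner FQHC clinics by an employee of the FQHC" (4.1). Every participant must be an "Active patient at selected Primary Health Network clinics" (3.1).

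Section 8.2 calls the study a pilot to approximate the screening rates and to inform later, better-powered studies. Assuming 40% against 20%, it says that "the proposed sample sizes yield 80% power based on a two-sided Fisher's exact test and a 2.5% type-1 error rate". Section 8.1 gives the numbers: "110 will be randomized to the control group and 110 will be randomized to the intervention group", with about 10% lost to follow-up.

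The documents do not describe checking a reported screening against any record. They do not say how survey and kit data combine into the overall rate, which source prevails if they disagree, or how a woman without a follow-up survey is counted.

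**The concern.** The two arms' rates come from different kinds of evidence. An intervention screening done by kit leaves a laboratory result; a control screening leaves only a statement on the telephone.

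It is easy to assume that over-reporting cancels because both arms answer the same survey. At equal rates it does not. Only an unscreened woman can over-report, and at the design rates 80% of controls are unscreened against 60% of the intervention arm. The same tendency therefore adds more false events to the control arm.

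Missing data are uneven in the same way. A 10% loss is about 11 women per arm (0.10 x 110). The controls among them have no outcome at all, while those in the intervention arm may still have kit results.

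Both co-primary differences are exposed, and so is the control rate that a later trial would be planned on.

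**Working it through.** **Inputs from the plan.** True rates pI = 40% and pC = 20%, two-sided Fisher's exact test at 2.5% (8.2); 110 per arm and about 10% loss, leaving 110 x 0.9 = 99 (8.1).

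**Assumed input.** f is the share of unscreened women who report a screening. The documents give no value, so 5%, 10% and 20% are shown.

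**The plan's own figure.** Enumerating Fisher's test over both binomial distributions gives 81.3% power at 110 per arm, which agrees with the stated 80%. At 99 per arm it is 76.3%. That drop comes from attrition and is separate from this point.

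**Equal over-reporting.** Each arm reads p + f(1 - p), so the observed difference is (pI - pC)(1 - f) = 20(1 - f) points. For f = 10%: intervention 40 + 0.10 x 60 = 46%; control 20 + 0.10 x 80 = 28%; difference 18 points.

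| Assumed f, both arms | Intervention reads | Control reads | Difference (points) | Power, 110 per arm | Power, 99 per arm |
|---|---|---|---|---|---|
| 0 | 40% | 20% | 20 | 81.3% | 76.3% |
| 5% | 43% | 24% | 19 | 73.6% | 68.0% |
| 10% | 46% | 28% | 18 | 65.3% | 59.6% |
| 20% | 52% | 36% | 16 | 50.7% | 46.4% |

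**Unequal over-reporting.** With rates fC and fI, the difference is 20 - 80fC + 60fI points. It exceeds 20 when fI > (80/60)fC, that is, above 1.33 times the control rate. With fC = 10% and 110 per arm:
- fI = 5%: 43% against 28%, 15 points, power 48.0%.
- fI = 0: 40% against 28%, 12 points, power 30.9%.
- fI = 20%: 52% against 28%, 24 points, power 90.0%.

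**Effect on the control rate.** It reads 20 + 80f per cent whatever happens in the other arm. Forgotten screenings work the other way: if a share u of screened controls fail to report, the rate becomes 20(1 - u) + 80f. It is inflated whenever 80f > 20u, which is what net over-reporting means here.

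**Check on a records-only remedy.** Suppose the records miss an assumed share m of clinic screenings, and cI is the clinic-based screening rate in the intervention arm. The observed difference is (pI - m cI) - (1 - m)pC = 20 + m(pC - cI) points. With m = 25% and cI = 0, the result is 40% against 20 x 0.75 = 15%, or 25 points. A records-only outcome can therefore overstate the effect.

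**The case against.** The strongest reply is that neither the direction nor the size is established. The survey feeds both arms, and the plan does not say that kit data override it. Intervention women were sent kits and asked to use them, so they might over-report more than controls, and above 1.33 times the control rate the difference widens. That stands: a reader might infer that the difference must shrink, and the documents do not support that.

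A reader might also take the case in which only controls over-report as the expected one. It requires that kit return alone decide the intervention outcome, which section 8.3 does not say. It is a bound.

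The power loss is conditional too. Section 8.2 does not call 40% and 20% true rates. If they are the rates expected under the planned survey, no power is lost against the plan's assumption. The analysis is also described as primarily descriptive, which gives power less weight. The control rate would still be biased as an estimate of actual screening.

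Replacing self-report with records would not be neutral. Kits reach the study laboratory from the intervention arm only, and screenings done elsewhere and missed by the records would fall mainly on controls. This objection stands and shapes the fix.

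Finally, the absence of verification is read from silence. The survey instruments and the Research Data Plan Review Form cited in section 22 are not among the documents. Nor do the documents say whether the interviewer knows the woman's arm, so no conclusion is drawn from that.

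**Conclusion.** The point holds in a limited form. As written, control-arm events rest on unconfirmed self-report, kit-based intervention events rest on laboratory evidence, and unreached controls have no outcome. That imbalance follows from sections 7.2.3, 7.2.5, 7.4.4 and 8.3 without any assumed figure.

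Net over-reporting inflates the control rate: at an assumed f of 5%, 10% or 20% it reads 24%, 28% or 36% instead of 20%. With equal f in both arms and 40% and 20% taken as true rates, the difference falls to 19, 18 or 16 points and power at 110 per arm to 74%, 65% or 51%. These sizes illustrate the exposure and do not predict the result, since the documents give no f and unequal over-reporting could move the difference either way. The change is worth making before follow-up closes because it is cheap for a pilot whose purpose is to supply these rates.

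**What to change.** In section 8.3:

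- Add one query of the health centers' electronic records at the end of follow-up, for all randomized women in both arms, including those not reached by phone, covering randomization to week 10. Staff there already search these records for eligibility, and all participants are active patients of the clinics.
- State one rule, applied alike in both arms, for combining laboratory, record and survey data. Kit use counts only if the laboratory received the kit; a reported clinic screening is checked against the record.
- Report both co-primary differences two ways: record-confirmed (laboratory or electronic record), and with unconfirmed self-reported screenings included. Collect the date and place of each reported screening. Self-report is kept because records alone can overstate the effect.

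In section 6, extend the wording so that the authorization covers the query. Section 6.2.2 now justifies health information for processing tests, mailing and compensation, and 6.2.3 describes all data collection as by telephone.

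The cost is one more query and an IRB-reviewed wording change. The record-confirmed version will miss some screenings done outside the clinics; the second version shows how much that matters.

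### Fisher's exact test is valid but conservative for the two primary endpoints; Boschloo's exact test at the same 2.5% level would add a few points of power, as an optional gain

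*Combined protocol and SAP*

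**What the plan says.** Section 1.2 sets two binary primary endpoints: the cervical and the colorectal screening rate at the end of the study, compared between arms. For the test, Section 8.3 says that "Analysis of the main outcomes will be evaluated with a Fisher's exact test". Section 8.2 assumes 40% screened in the intervention arm and 20% in the control arm, and says that the planned numbers "yield 80% power based on a two-sided Fisher's exact test and a 2.5% type-1 error rate", the 2.5% allowing for the two endpoints. Section 8.1 states that "110 will be randomized to the control group and 110 will be randomized to the intervention group" and adds: "We expect about 10% loss to follow-up over the study period". Section 7.2.2 describes the allocation: "A simple randomization scheme, with 1:1 randomization, will be used to ensure equal sample sizes in the intervention and control arms".

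No reason is given for choosing Fisher's test, and no other exact test is mentioned. The two-sided p-value is not defined. It could be the minimum-likelihood version, which sums all tables no more likely than the one observed, or twice the smaller one-sided p-value. Section 8.3 also calls the analysis primarily descriptive, and Section 8.2 calls the study a pilot.

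**The concern.** Fisher's test conditions on the total number of women screened. In a trial with two independent arms that total is random, and fixing it leaves few attainable p-values. The rejection probability under the null therefore stays below the nominal level.

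Boschloo's test takes the Fisher p-value as its statistic. It sets the cutoff so that the maximum rejection probability, over every possible common screening rate, stays within 2.5%. Its rejection region contains Fisher's, so for a given two-sided definition it cannot have lower power.

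What is at stake is a few points of power in a trial that is sized to just above 80% before any loss. In a borderline result, the choice of test could decide whether a difference is reported as significant.

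**Working it through.** **Inputs.** Rates of 40% and 20%, two-sided 2.5% per endpoint (Section 8.2); 110 per arm and about 10% loss (Section 8.1). If the loss is equal and leaves the analysis, 110 × 0.9 = 99 per arm remain.

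**Method.** Every 2×2 table was enumerated under two independent binomials. Power is the sum of Bin(x; n1, 0.40) × Bin(y; n2, 0.20) over the tables (x, y) that the test rejects. True size is the same sum with one common rate p in both arms, maximised over p from 0.001 to 0.999. Fisher rejects if its p-value is at most 0.025. Boschloo rejects if the Fisher p-value is at most c, where c is the largest cutoff with maximum size no greater than 0.025.

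**Plan's own figure.** Fisher at 110/110 has 81.3% power, so the stated 80% reproduces, with no allowance for loss.

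**Equal arms.** Both two-sided definitions give the same result.

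| n per arm | Fisher power | Fisher max. size | Boschloo cutoff c | Boschloo power | Boschloo max. size |
|---|---|---|---|---|---|
| 110 | 81.3% | 1.81% | 0.0307 | 83.5% | 2.46% |
| 99 | 76.3% | 1.88% | 0.0323 | 79.5% | 2.48% |

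- Gain: 83.5 − 81.3 = 2.2 points at 110 per arm, and 79.5 − 76.3 = 3.2 points at 99.
- At common rates of 20% to 40%, Fisher's true size is 1.6 to 1.7% for both arm sizes.
- Fisher needs 107 per arm for 80% power (106 gives 79.6%); Boschloo reaches 80.1% at 100.
- At 35% versus 20% with 99 per arm, power is 49.2% for Fisher and 53.3% for Boschloo.
- Example: 35/99 versus 20/99 gives Fisher p = 0.026, which misses 2.5%, and Boschloo p = 0.019, which does not.

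**Check by normal approximation.** Power is Φ[(0.20 − 2.241 × √(0.42/n)) / √(0.40/n)], with 0.42 = 2 × 0.3 × 0.7 and 0.40 = 0.24 + 0.16. At n = 99 this is Φ[(0.20 − 2.241 × 0.0651) / 0.0636] = Φ(0.85) = 80.2%; at n = 110 it is 84.6%. Boschloo lies about one point below these values; Fisher lies 3 to 4 points below.

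**Unequal arms** (intervention first; gains taken before rounding).

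| Arms | Minimum likelihood: Fisher → Boschloo (gain) | Doubled one-sided: Fisher → Boschloo (gain) |
|---|---|---|
| 97/101 | 79.2% → 81.0% (1.9) | 75.9% → 79.6% (3.7) |
| 104/94 | 78.0% → 79.5% (1.4) | 76.1% → 80.1% (4.0) |
| 92/106 | 78.8% → 79.6% (0.8) | 74.7% → 79.4% (4.7) |
| 106/92 | 77.3% → 80.1% (2.8) | 76.0% → 80.0% (4.1) |
| 94/110 | 79.0% → 81.6% (2.5) | 79.0% → 80.2% (1.2) |
| 110/99 | 80.7% → 81.3% (0.6) | 78.8% → 82.5% (3.7) |

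With unequal arms Fisher's maximum size is about 2.1 to 2.3% by minimum likelihood (105/115: 2.12%; 98/100: 2.25%) and about 1.7 to 1.9% by doubling. Boschloo's stays within 2.5% throughout. With the same p-value definition, no table rejected by Fisher was lost in any split.

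**The case against.** The strongest reply is that nothing in the plan is wrong. Fisher's test controls type I error, Sections 8.2 and 8.3 name the same test, and the stated power reproduces. A standard, easily explained test is a legitimate choice. The study is a pilot with a primarily descriptive analysis, and the test changes neither the estimated rates nor their difference. All of this stands and lowers the importance of the point. It does not remove it, because Section 8.2 sets an alpha and a power for two co-primary endpoints and Section 8.3 names the test that will be reported.

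Three stronger readings are tempting, and the documents do not support them.

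- *That Fisher's true size never exceeds about 1.8% in this trial.* This needs arms of exactly 110. Section 7.2.2 specifies simple randomization, which does not guarantee equal arms. If each woman is allocated independently, the size of one arm has standard deviation √(220 × 0.5 × 0.5) = 7.4, so a split such as 105/115 is ordinary. By minimum likelihood its maximum size is 2.12%.
- *That power after loss is 76% and Boschloo restores 80%.* This assumes that the loss is equal and that lost women leave the analysis, which the plan does not say. Section 8.3 also counts kit return, which is known from the laboratory (Section 7.4.4) without a follow-up survey, and Section 3.3.2 allows withdrawn women to be replaced. If loss removed only control women (110/99), the gain would be 0.6 points by minimum likelihood or 3.7 by doubling.
- *That the change of test deals with loss to follow-up.* The absence of any inflation for loss is a separate matter; a better test only offsets part of it.

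**Conclusion.** The point holds as an optional efficiency gain. At the plan's own rates and level, Boschloo's test adds about 2 points of power at 110/110 and about 3 points at 99/99, with exact control at 2.5%. The second figure assumes equal loss that leaves the analysis.

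With unequal arms the gain depends on the two-sided definition. It is mostly 0.6 to 2 points by minimum likelihood (up to 2.8 in the splits examined) and mostly 3 to 4 by doubling (range 1.2 to 4.7). It was positive in every split examined. At equal arms near 100 it is worth about 107 − 100 = 7 evaluable women per arm.

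The conclusions rest on independent binomial outcomes and the 40% and 20% assumptions. A reader should not infer that the planned test is invalid or that the power statement is wrong.

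**What to change.** Before any outcome data are seen:

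- **Section 8.3:** name the two-sided Boschloo unconditional exact test for each primary endpoint at 2.5%. State whether it is built on the minimum-likelihood or the doubled one-sided Fisher p-value, and check that the software uses that version. Keep Fisher, with the same p-value definition, as a sensitivity result; the guarantee that no Fisher rejection is lost applies only within one definition.
- **Section 8.2:** restate power for that test as 83.5% at 110 per arm and about 79.5% at 99 evaluable per arm. Label both as equal-arm figures at 40% versus 20%, and the second as assuming that lost women leave the analysis.

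The cost is a short edit in each section. No extra participants, data or procedures are needed, and the test is in standard software. The drawback is a less familiar test that will need a line of explanation in the report.
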